12.2 Derived and transformed data

Baseline will be considered to be the latest value obtained before study drug administration (eg before dosing on Day 0, or Screening if not recorded at predose on Day 0 or Day -3).

Laboratory data will be reported in standard units. Out-of-range laboratory tests may be repeated. If a test is out-of-range at baseline and repeated before dosing, the latest repeat value before dosing will be used as baseline. However, if a test is out-of-range and repeated at any other time during the study, the out-of-range value (not the repeat value) will be included in statistical summaries.

Triplicate electrocardiogram (ECG) measurements will be taken on screening and the mean of the 3 measurements will be used for analysis. Triplicate vital sign measurements at baseline and the mean of the 3 measurements will be used for analysis.

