Changes in drinking behaviour including alcohol intake and cravings will be assessed weekly until Day 84 using the Alcohol TLFB and ACQ. Alcohol craving will also be assessed using a Craving VAS before and after dosing on Day 0.

Markers of alcohol use will be assessed at multiple timepoints, e.g., breath (Day 0 only), blood (Screening, Day – 3, 28 and 84) and urine (Screening and Days 1, 28, 56, and 84).

Alcohol withdrawal symptoms using CIWA-Ar will be assessed at Day 0.

Quality of life will be assessed by EQ-5D-5L at Screening and Days 28 and 84.

Patients will be invited to complete an optional semi-structured interview on Days 1 and 84 and to complete optional online psychological change questionnaire on Days -3, 1, 28, and 84.

Details of the methodology, interview structure and psychological changes measures can be found in the Psychological Change Study Manual.

Statistical methods:

[figure not shown]
This is an exploratory study and there are no null hypotheses to be tested.

Summary statistics will be presented for all function and safety parameters.

In general, descriptive statistics including number of observations, mean, standard deviation, median, minimum, and maximum will be presented for continuous parameters. Categorical parameters will be displayed using counts and percentages within each category.

Additional information is provided in the protocol. Full details of the statistical analysis will be provided in the statistical analysis plan (SAP).

Figure 1: Study Flow Diagram

NOTE: Patients will receive ongoing AUD relapse prevention psychotherapy throughout the study.

SCHEDULE OF EVENTS

TABLE 1: SCHEDULE OF EVENTS

Assessments/Procedures	Screening ¹	Psychedelic Preparation ² (In clinic or video call)			Dosing ³	Follow-up												
	Day -28 to -14	Day -12	Day -7	Day -3	Day 0	Day 1	Day 7	Day 14	Day 21	Day 28	Day 35	Day 42	Day 49	Day 56	Day 63	Day 72	Day 77	Day 84
		(± 5 days)		+2days		(± 2 days)			(± 4 days)									
General																		
Informed consent	X																	
Confirm eligibility	X				X													
Medical history	X																	
Demographics	X																	
Height/weight	X				X													X
Concomitant medication	X	X	X	X	X	X	X	X	X	X	X	X	X	X	X	X	X	X
Physical examination	X									X				X				X
Vital signs (HR, BP, and temperature) ⁴	X				X	X												X
ECG ⁷	X				X	X												X
Cardiac telemetry ²³					X													

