3.3. Exploratory Endpoints

Pharmacokinetic:

- Blood samples to determine 5-MeO-DMT and its metabolites (including bufotenine) plasma concentrations will be taken after dosing on Day 0.

Drinking Craving:

- Change in alcohol craving as measured by Alcohol Craving Questionnaire (ACQ) at Days 1, 7, 28, 56, and 84 compared to Baseline (pre-dose on Day 0)
- Alcohol cravings as measured by Craving Visual Analogue Scale (VAS)
- Alcohol withdrawal symptoms as measured by Clinical Institute Withdrawal Assessment (CIWA-Ar)
- Consequences of alcohol use as measured by Short Inventory of Problems (SIP)

Alcohol Use:

Using the Timeline Follow-Back (TLFB) interview, the following parameters of alcohol use in the 90 days before dosing and endpoint will be recorded:

- Percentage of Heavy Drinking Days (PHDD) in 85d prior D-3 (or start of detox) vs PHDD post-dosing measured on d14, d28, d56, d84.
- Percentage of drinking days (PDD) in 85d prior D-3 (or start of detox) vs PDD post-dosing measured on d14, d28, d56, d84.
- Mean Units per day (UPD): In 85d prior D-3 (or start of detox) vs UPD post-dosing measured on d14, d28, d56, d84.
- Abstinence: Percentage of Abstinent days (PAD) in 85d prior D-3 (or start of detox) vs PAD on d14, d28, d56, d84 (with biomarker verification).
- Longest duration (days) of continuous abstinence
- Number of days after BPL-003 dosing to first drink
- Number of days after BPL-003 dosing to first HDD (defined by UK government as >7 units a day for a woman and >9 units per day for a man)
- Average number of standard units of alcohol consumed per week in 85d prior D-3 (or start of detox) vs post-dosing measured on d14, d28, d56, d84 (and reported referencing UK risk levels)
- Maximum number of standard units of alcohol consumed on any one day

Correlation of PD effects with alcohol use and related symptoms

The correlation of the occurrence of a “complete mystical experience” and “ego dissolution”, measured by the MEQ30 and EDI, with improvement in alcohol use and craving (measured by AQC, TLFB, EtG, CDT)

Biomarkers

- Alcohol use as measured by EtG in urine at Days 1, 28, 56, 84 compared to Screening
- Alcohol use as measured by CDT in blood at Days 28 & 84 compared to Screening

Wellbeing

- Change in Montgomery–Asberg Depression Rating Scale (MADRS) at Days 28, 56, and 84 compared to Baseline
- Change in Clinical Global Impression Severity (CGIS) at Days 1, 28, 56, and 84 compared to Baseline

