9.17.2. Carbohydrate Deficient Transferrin

Chronic alcohol use causes a transient change in the glycosylation pattern of transferrin, where the relative amounts of disialo- and asialotransferrin (carbohydrate deficient transferrin [CDT]) are increased over the amount of normally glycosylated tetrasialotransferrin. CDT can be used to detect whether someone is a binge drinker or a daily heavy drinker (4 or more drinks a day) ([Fleming, 2004](#)). It can even be used to determine AUD relapse ([Mitchell, 1997](#)). Generally, CDT levels will return to normal within several weeks of abstinence of alcohol use. CDT testing alone is not recommended for general screening for AUD; however, when combined with other assessments (e.g.: gamma-glutamyl transpeptidase [GGT], alanine aminotransferase [ALT], aspartate aminotransferase [AST], mean corpuscular volume [MCV], EtG, and patient self-reporting), clinicians can expect to identify the majority of patients with AUD ([Gough, 2015](#)).

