4.2.3 Exploratory endpoint(s)

Pharmacokinetic:

- Blood samples to determine 5-MeO-DMT and its metabolites (including bufotenine) plasma concentrations will be taken after dosing on Day 0.

Drinking Cravings and withdrawal:

- Change in alcohol craving as measured by Alcohol Craving Questionnaire (ACQ) at Days 1, 7, 28, 56, and 84 compared to Baseline (pre-dose Day 0)
- Alcohol cravings as measured by Craving Visual Analogue Scale (VAS)
- Alcohol withdrawal symptoms as measured by Clinical Institute Withdrawal Assessment (CIWA-Ar)

Alcohol Use:

- Using the Timeline Follow-Back (TLFB) interview, the following parameters of alcohol use in the 90 days before dosing and endpoint will be recorded:
 - Longest duration (days) of continuous abstinence
 - Maximum number of standard units of alcohol consumed on any one day
 - Number of Heavy Drinking Days (HDD)
 - Percentage of Heavy Drinking Days (PHDD) in 85d prior D-3 (or start of detox) vs PHDD post-dosing measured on d14, d28, d56, d84
 - Percentage of drinking days (PDD) in 85d prior D-3 (or start of detox) vs PDD post-dosing measured on d14, d28, d56, d84.
 - Mean Units per day (UPD): In 85d prior D-3 (or start of detox) vs UPD post-dosing measured on d14, d28, d56, d84.
 - Abstinence: Percentage of Abstinent days (PAD) in 85d prior D-3 (or start of detox) vs PAD on d14, d28, d56, d84 (with biomarker verification).
 - Number of days after BPL-003 dosing to first drink
 - Number of days after BPL-003 dosing to first HDD (defined by UK government as ≥ 7 units a day for a woman and ≥ 9 units per day for a man)
 - Average number of standard units of alcohol consumed per week in 85d prior D-3 (or start of detox) vs post-dosing measured on d14, d28, d56, d84 (and reported referencing UK risk levels)
- Consequences of alcohol use as measured by Short Inventory of Problems (SIP)
- Biomarkers:
 - Alcohol use as measured by Ethylglucuronide (EtG) in urine at Days 1, 28, 56, 84 compared to Screening
 - Alcohol use as measured by carbohydrate deficient transferrin (CDT) in blood at Days 28 & 84 compared to Screening

Pharmacodynamic

- The correlation of the occurrence of a “complete mystical experience” and “ego dissolution”, measured by the MEQ-30 and EDI, with improvement in alcohol use and craving (measured by ACQ, TLFB, EtG, CDT)

Wellbeing:

- Change in Montgomery–Asberg Depression Rating Scale (MADRS) at Days 28, 56, and 84 compared to Baseline

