14.7 Clinical laboratory evaluations

Data from haematology, coagulation, clinical chemistry and alcohol biomarkers at each planned assessment, and changes from baseline at each planned post baseline assessment, will be summarised by treatment.

Clinically significant abnormal laboratory tests will be listed. Frequencies of clinically significant postpose abnormal laboratory tests will be summarised.

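### The exploratory CDT endpoint is stated against Screening, but the SAP's general baseline rule makes Day -3 the comparator in the planned change column

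*SAP*

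**What the plan says.** **Endpoint.** Protocol 3.3 lists "Alcohol use as measured by CDT in blood at Days 28 & 84 compared to Screening". SAP 4.2.3 repeats it: "Alcohol use as measured by carbohydrate deficient transferrin (CDT) in blood at Days 28 & 84 compared to Screening". In the same lists, ACQ, MADRS, CGIS and EQ-5D-5L are referred to Baseline. Only the two alcohol biomarkers, CDT and urine EtG, are referred to Screening.

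**Sampling.** The Methods part of the protocol synopsis gives the blood markers of alcohol use as "blood (Screening, Day – 3, 28 and 84", which agrees with the CDT row of protocol Table 1. CDT therefore has two pre-dose values and none on Day 0. In Table 1, EtG has one pre-dose sample, at Screening.

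**Baseline rule.** SAP 12.2 states: "Baseline will be considered to be the latest value obtained before study drug administration". It then allows for a missing value: "or Screening if not recorded at predose on Day 0 or Day -3". Protocol 11.6 has the same rule.

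**Output.** SAP 14.7 will summarise "alcohol biomarkers at each planned assessment, and changes from baseline at each planned post baseline assessment". The table list assigns the biomarkers to Table 14.3.5.4, template T_LB2, which shows descriptive statistics by planned time and one block of changes from baseline. SAP Appendix A has no biomarker entry. Section 17 declares one change from the protocol analysis, about laboratory flags, and nothing about the CDT comparator.

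**The concern.** Followed literally, the SAP tabulates a different quantity from the one its endpoint names, and it does not say so. A programmer working from sections 12.2 and 14.7 would subtract Day -3, while a reader starting from section 4.2.3 would take the column as a change from Screening.

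The interval between the two samples is not inert. Relapse-prevention therapy starts during the preparation sessions (protocol Table 1, note 15, and Appendix 4). Drinking is restricted shortly before dosing. Protocol 9.17.2 says that "CDT levels will return to normal within several weeks of abstinence of alcohol use". A fall in CDT before dosing is therefore possible, and the two comparators would treat it differently. Screening would count it in a result reported after BPL-003, and Day -3 would leave it out. With at most 12 patients, an unlabelled choice between them could alter how the biomarker is described.

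**Working it through.** The plan states no figure to reproduce, so the check applies the rule to the schedule.

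**1. Which sample is baseline**

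| Biomarker | Pre-dose samples (Table 1) | Baseline under SAP 12.2 | Comparator in SAP 4.2.3 | Agree? |
|---|---|---|---|---|
| CDT | Screening, Day -3 | Day -3 | Screening | No |
| Urine EtG | Screening | Screening | Screening | Yes |

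One table would therefore carry two biomarkers with different reference points under a single column heading.

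**2. What the change column leaves out.** For each patient:

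(post-dose − Screening) = (post-dose − Day -3) + (Day -3 − Screening)

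The endpoint names the left-hand side. The planned column gives the first term on the right. The second term appears in no change column.

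**3. Length of the omitted interval.** The Screening column of Table 1 is headed Day -28 to Day -14. The last preparation visit is Day -3 with a window of +2 days, so no later than Day -1.

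- Shortest nominal gap: −3 − (−14) = 11 days
- Longest nominal gap: −3 − (−28) = 25 days
- Longest gap with the window: −1 − (−28) = 27 days

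**4. Illustration with assumed values, not document figures.** Take Screening 3.0 and Day 28 1.8.

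- If Day -3 is 2.2, the change from Screening is 1.8 − 3.0 = −1.2. The planned column shows 1.8 − 2.2 = −0.4. The pre-dose part, 2.2 − 3.0 = −0.8, is not in the column.
- If Day -3 is 3.0 (no pre-dose fall), both changes are −1.2 and the comparator makes no difference.

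The documents do not say where between or beyond these cases the trial's patients will lie.

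**5. Mixed comparators.** SAP 12.2 falls back to Screening when Day -3 is missing. Two patients with the same assumed course (3.0, 2.2, 1.8) would contribute −0.4 if the Day -3 sample exists and −1.2 if it does not, under one label.

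**The case against.** The strongest reply is that little information is lost. T_LB2 gives observed statistics at every planned time, so Screening and Day -3 means should both appear, and complete data listings are promised at the end of SAP 19.1. With at most 12 patients, each difference from Screening can be worked out by hand. The CDT endpoint also asks for a comparison with Screening without using the word change, and by-visit summaries partly supply that. All of this stands. A reader might infer that the pre-dose movement vanishes from the report, and the documents do not support that. What is missing is the paired change and its spread, which two visit means do not give.

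A second reply is that Day -3 is the better reference for post-dose change, because a Screening comparator would let a pre-dose decline be credited to the drug. This is fair, and it is a reason to show both changes or to amend the endpoint. It does not justify leaving the endpoint and the output in disagreement.

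A third reply is that this is one exploratory, descriptive biomarker. That also stands: no primary or secondary result, error rate or sample size is touched.

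**Conclusion.** The mismatch holds. It is internal to the SAP (4.2.3 against 12.2, 14.7 and T_LB2), and it also sets the protocol's endpoint against the planned output. It rests only on the text and the sampling schedule. Its extent is one exploratory biomarker, one change column and a pre-dose interval of 11 to 25 days (up to 27). It should be corrected, but it threatens no main conclusion.

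Two stronger readings are not supported:

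- **That most of the CDT fall occurs before Day -3.** The documents give no rate of decline, only a return to normal over several weeks of abstinence. They do not require abstinence from Screening. Heavy drinking is ruled out for 72 hours and any alcohol for 24 hours before dosing, and protocol 6.6 leaves room for patients with some alcohol in their system to attend preparation. If drinking continues, the pre-dose fall may be near zero. Inclusion criterion 5 also allows the last heavy drinking day, or the end of detoxification, to lie up to 14 days before Screening, so some decline may precede both samples.
- **That change from Day -3 isolates the drug.** It is the only part that could contain a drug effect. In a single-arm, open-label study it stays confounded with weekly relapse-prevention psychotherapy and with continuing decline from any drinking reduction before dosing.

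**What to change.** In SAP 14.7 and Table 14.3.5.4, override the general baseline for CDT and report three labelled paired changes:

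1. Screening to Days 28 and 84: the stated endpoint.
2. Screening to Day -3: pre-dose change.
3. Day -3 to Days 28 and 84: post-dose change.

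A patient with no Day -3 sample would contribute to the first change only, so no column mixes comparators. A footnote should give the EtG reference as Screening. A second footnote should say that the third change is the only one that could contain a drug effect, and that it cannot be separated from psychotherapy or from decline already under way.

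Alternatively, amend the CDT endpoint to use Day -3 and record that in SAP section 17.

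The cost of the first option is a sentence or two in the SAP, two footnotes and a few extra rows in one table. All the samples are already scheduled, and no study procedure changes.

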12.3 Assessment windows

No assessment windows are defined for this report.

12.4 Values of potential clinical importance

A vital signs result will be considered to be of potential clinical importance (PCI) if it falls outside the relevant range below:

Vital Sign	Range
Systolic blood pressure	90–140 mm Hg
Diastolic blood pressure	40–90 mm Hg
Pulse rate	40–100 beats/min
Temperature	35.5–37.8°C

QTcF > 450 msec and increases in QTcF from baseline (Day 0, predose) of > 30 msec will be considered to be of PCI.

13 Study population

13.1 Disposition of patients

The disposition of all patients in all populations will be summarised including: number of patients consented, number of patients treated; number completing the study, by treatment; and number withdrawn from the study. The number of screen failures will also be listed and summarised including reason for screen failure.

All patients who withdraw or are withdrawn from the study will be listed, by treatment, with the reason for withdrawal.

A listing of analysis populations will be provided.

13.2 Protocol deviations

Protocol deviations are captured and reviewed (including classification as minor or major) on an ongoing basis during the study, as defined in the Protocol Deviation Plan. Before closing the database, a final review of the protocol deviations will be conducted and an assessment completed to identify any important deviations where data should be excluded from analysis populations.

Potential important protocol deviations are detailed in the Protocol Deviation Plan.

In addition, patients with minor time deviations (measurements taken outside the allowable windows) will be identified. Allowable time windows for pharmacokinetic samples and other procedures are given in Section 6.6 of the study protocol.

Protocol deviations (including time deviations) will be listed by classification and category.

13.3 Demographic and baseline characteristics

Demographic and baseline characteristics will be listed and summarised.

Patients who take concomitant medication will be listed. All non-trial medication will be coded using the latest version of the World Health Organisation (WHO) Drug Global dictionary current at the time of database lock (version March 2024 or higher).

Medical history data will be coded using the version of the Medical Dictionary for Regulatory Activities (MedDRA) which is current at the time of database lock (version 27.0 or higher). All medical history data will be listed.

Alcohol use data (AUD DSM-V score, AUD severity, age of patient when they first recognised a drinking problem) will be listed and summarised. Other drug abuse lifetime use data will also be listed separately and summarised where applicable.

13.4 Treatment compliance

Dates and times of dosing will be listed.

14 Safety analyses

Summaries and listings of safety data will use the safety population.

14.1 Extent of exposure

The dates and times of treatment dosing will be listed to indicate exposure to the study medication.

14.2 Adverse events

AEs will be coded using the version of the MedDRA which is current at the time of database lock (version 27.0 or higher).

All AEs will be listed.

The number of patients with at least one treatment-emergent adverse event (TEAE) per treatment will be tabulated by actual treatment and MedDRA system organ class. A TEAE is defined as an event emerging during treatment (having been absent pre-treatment) or that worsens after treatment¹.

For each of the following, the number of TEAEs and the number of patients with TEAEs will be summarised:

- TEAEs, by system organ class and preferred term
- TEAEs, by system organ class and preferred term and by severity
- Drug-related (“probably” or “possibly” as recorded by the investigator) TEAEs, by system organ class and preferred term.

In addition, a summary of TEAEs by day of onset (Day 0, Days 1-6 and Day 7 or later) will be produced.

Patients with more than one TEAE will be counted only once, at the greatest severity or causality, for each system organ class/preferred term. Multiple TEAEs in a patient will be counted once per system organ class and preferred term. AEs with missing severity and/or causality will be treated as severe and possibly related, respectively.

Summaries will be sorted by system organ class and decreasing total incidence of preferred term.

14.3 Deaths, serious adverse events and other significant adverse events

Deaths and serious adverse events (SAEs) will be listed separately (fatal events separate from non-fatal events). Other significant AEs, as identified by the investigator in the CRF, will be listed separately.

14.4 Adverse events leading to withdrawal from the study

AEs leading to withdrawal will be listed separately.

14.5 Adverse events of special situations (AESS)

AESSs will be listed separately.

14.6 Adverse events of special interest (AESI)

AESIs will be listed separately.

14.7 Clinical laboratory evaluations

Data from haematology, coagulation, clinical chemistry and alcohol biomarkers at each planned assessment, and changes from baseline at each planned post baseline assessment, will be summarised by treatment.

Clinically significant abnormal laboratory tests will be listed. Frequencies of clinically significant postpose abnormal laboratory tests will be summarised.

